1.0 PROTOCOL SUMMARY AND/OR SCHEMA

This is an investigator initiated, open label, single institution basket study of the oral progesterone antagonist, onapristone ER (Apristor), alone or in combination with anastrozole, in women with selected progesterone receptor positive (PR+) recurrent gynecologic cancers. This study will enroll women with recurrent or advanced granulosa cell tumor, low grade serous ovarian cancer, or endometrioid endometrial cancer who have measurable disease and have progressed following at least one prior line of chemotherapy. Eligible patients will be progesterone receptor positive by immunohistochemistry (IHC), defined as \geq 1% positivity displayed on archival tissue. Biopsy will be performed if no archival tissue is available or if archival tissue was taken more than 3 years prior .

Cohorts will be defined by histology with Cohort 1 enrolling patients with granulosa cell tumor to treatment with single agent onapristone ER 50 mg PO BID, Cohort 2 enrolling patients with low grade serous ovarian cancer to treatment with single agent onapristone ER, and Cohort 3 enrolling patients with endometrioid endometrial cancer to treatment with single agent onapristone ER. Cohorts 2 and 3 were closed to accrual in March of 2021 due to poor accrual as new treatments have become available for these diseases during the course of this study (endometrioid accrued 1 patient, low grade serous ovarian cancer accrued 5 patients). Cohort 1 completed accrual to stage 1 and has shown stable disease in 9 out of 14 patients patients with recurrent PR+ granulosa cell cancer treated with single agent onapristone ER at 50mg PO BID with ongoing responses lasting > 9 months in 2 patients. However, no RECIST 1.1 Criteria complete or partial responses have been seen. Cohort 4 will enroll patients with PR+ granuloasa cell tumor to onapristone ER 50mg PO BID in combination with anastrozole 1mg PO daily.

	Treatment	Histology	Stage I	Stage II (expansion)	Response rate to be deemed worthy of further study
Cohort 1	Onapristone ER	PR+ Granulosa cell tumor	Enroll 14 patients, if ≥ 1 response(s) expand to Stage II	Expand to a total of 23 patients	≥ 3/23
Cohort 2	Onapristone ER	PR+ Low grade serous ovarian cancer	Enroll 16 patients, if ≥ 2 responses expand to Stage II	Expand to a total of 25 patients	≥ 5/25
Cohort 3	Onapristone ER	PR+ Endometrioid endometrial cancer	Enroll 19 patients, if ≥4 responses expand to Stage II	Expand to a total of 36 patients	≥ 11/36

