The PK and food effect study results from a phase I study in healthy subjects observed a half-life $(t_{1/2})$ of 4.2h for an oral immediate-release (IR) formulation of onapristone administrated in fasting conditions. The same study observed a minor food effect on the maximum plasma concentration (C_{max}) of onapristone and its metabolite M1 with an approximate average decrease of 18% and an average increase in AUC_{∞} of approximately 13%.

3.2 Prior Clinical Data with Onapristone from Breast Cancer Studies:

A non-randomized, open, multicenter phase 2 study was conducted between December 1991 and May 1995 at 13 sites in Germany and the United Kingdom[5]. The study goal was to investigate the efficacy and safety of onapristone when given 100 mg/day to post-menopausal women with advanced breast cancer that had progressed on tamoxifen. Of the 101 evaluable patients, one had a complete response (CR), 9 had a partial response (PR), and 39 had SD for three months or more. This resulted in an overall clinical benefit of 49%. The median duration of the CR + PR was 11 months and the median duration for patients with SD was seven months. The responses seen in the group of 33 evaluable patients with PR-positive primary tumors were promisimg with 4 (12%)patients displaying a partial response, 15 (45%) patients with stable disease.

A phase 2 study investigating onapristone as first-line endocrine therapy in patients with breast cancer was conducted as an investigator initiated study [6]. The study enrolled 19 patients before Schering AG closed the study in 1995 when the decision was made to halt the development of the immediate release formulation of onapristone.

Of the 19 patients entered into the study prior to study closure, one discontinued therapy after 4.5 months because of a marked elevation in the patient's LFT's. At that time, the patient had SD. The elevated LFTs rapidly returned to normal after discontinuation of onapristone. Of the remaining 18 patients, 10 (56%) showed a PR and two (11%) durable SD (≥6 months), giving an overall tumor benefit rate of 67%. The median duration of objective response and SD was 16.2 months. The majority of patients had hormone-receptor-positive tumors. Ten patients were ER-positive/PR-positive, of whom seven achieved PR, 1 had SD. Six patients had ER-positive/PR-negative tumors, of whom two achieved PR and two had SD. No response was seen in the remaining two patients who had ER-negative/PR-negative tumors.

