9.0 TREATMENT/INTERVENTION PLAN

9.1 Treatment Plan

Enrolled patients will initiate treatment with onapristone ER 50 mg by mouth twice daily, about 12 hours apart, and anastrozole 1mg po QD in AM (if in cohort 4) beginning Day 1 of Cycle 1. A Cycle is 28 days. Onapristine ER tablets should be swallowed whole with a glass of water and food I. Onapristone ER and anastrozole should be taken at the same times each day. Missed doses will not be made-up. Vomited doses should not be retaken. All doses and missed doses will be recorded in the patient's pill diary. Patients will remain on treatment with onapristone ER 50 mg PO BID alone (cohorts 1-3) or with anastrozole 1 mg po QD (cohort 4) (with dosage adjustments as described below) until POD, unacceptable toxicity or withdrawal of consent.

While on study, patients will return for assessments with a treating physician every 2 weeks during the first cycle, and then every 4 weeks. Vital signs, toxicity assessment and blood work will be performed at each start of cycle visit. The pill diary will be collected, and a new drug supply and pill diary will be provided. A +/- 4 day window is allowed for each start of cycle assessment.

Within 30 days of starting treatment, every 8 weeks from Cycle 1 Day 1 while on treatment, and at end of study, patients will have a CT of chest, abdomen and pelvis performed, or MRI of abdomen and pelvis with CT of chest. Best overall response should be confirmed with repeat imaging performed at \geq 4 weeks. There is a +/- 7 day window for completion of interval tumor assessments by imaging.

An optional research non-billable tumor biopsy will be performed at end of treatment in consenting patients with accessible disease.

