10.0 EVALUATION DURING TREATMENT/INTERVENTION

	Screening	Pre- Treatment ⁹	Day 1³; Cycle 1	Day 15; Cycle 1 ³	Day 1; Cycle 3, 5, 7 (odd cycles) ³	Day 1; Cycle 2, 4, 6 (even cycles) ³	End of Study Treatment Follow up⁵	Safety 30 day & Survival Follow up
Informed Consent	Х	Х						
History & Physical		Х	Х	X ⁷	X ⁷	X ⁷	Х	
Toxicity Assessment		Х	Х	Х	Х	Х	Х	X ¹¹
Vital Signs		X ¹	X ¹	X ¹	X ¹	X ¹	X ¹	
KPS		Х	X	Х	Х	X	X	
ECG		X ²						
Radiographic Tumor Assessment of Chest/ Abd/ Pelvis		X ⁴			X ⁴		X ⁴	
CBC with Differential		Х	X ¹⁰	Х	Х	Х	Х	
Pregnancy Test (for patients of child bearing potential)		Х				Х		
Comprehensive Metabolic Panel		X	X ¹⁰	Х	Χ	Х	X	
Coagulation Tests		Х						
Bone Density	Х							Every 12 months (±14 days)
Tumor Biopsy	X ⁶ , and IHC testing						X ⁶	
Dispense Onapristone ER (and anastrozole, if cohort 4)			X ⁸		X ₈	X ⁸		
Chart review for PD								Every 3 months (±14 days)
Survival status								Every 3 months (±14 days)

^{1:} Vital signs: blood pressure, heart rate, temperature and weight. Height need only be taken on Cycle 1, Day 1.

^{2:} Hypokalemia should be corrected prior to ECG collection

^{3:} All visits have a +/- 4 day window unless otherwise noted

- 4: Radiographic tumor assessment of abdomen and pelvis may be performed using CT or MRI. Chest imaging chould occur by CT. There is a +/- 7 day window for completion of interval tumor assessments by imaging. Imaging should be performed every 8 weeks following Day 1 of treatment. Radiographic tumor assessment at end of study treatment should only be completed for patients coming off study for reasons other than progression and only if it has been greater than 4 weeks since the last tumor assessment.
- 5: End of Study Treatment Visit should happen within 30 days of last dose of study drug.
- 6: Patients without adequate archival tissue from within the past 3 years available will have a biopsy performed, as medically appropriate for their disease. Patients who had progressive disease and consent for an end of treatment biopsy will have an optional non-billable tumor biopsy performed at end of treatment.
- 7: Includes recording of concurrent medications and focused physical exam. There is a +/- 4 day window allowable for each start of Cycle assessment.
- 8: Pill diary and remaining pills should be collected and new pill diary and 1 month supply of study drug should be given to patient. Anastrozole will be prescribed by the treating physician and dispenced as commercial supply.

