- 9: Screening assessments should be completed within 30 days prior to treatment with the exception of CBC with differential, comprehensive metabolic panel, coagulation tests, and pregnancy test which should be completed within 14 days prior to treatment.
- 10: Cycle 1 Day 1 blood tests can be omitted if Screening blood tests are completed within 72 hours from Cycle 1 Day 1.
- 11: A safety follow-up visit or phone call will be conducted 30 days (± 7 days) after the last dose of onapristone ER. AE should be monitored.
- 12: Survival follow-up phone call will be conducted every 3 months from 30 day safety follow-up visit until the patient initiates a new treatment.

For the patients who came off treatment due to unacceptable toxicity or withdrawal of consent, reviewing medical records for progression status will stop once the patient becomes POD.

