13.0 CRITERIA FOR REMOVAL FROM STUDY

Study treatment will be discontinued for the following reasons:

- Progression of disease (unless patient agrees to continue treatment past progression)
- Persistent or unacceptable toxicity despite appropriate dose reductions
- · Withdrawal of consent
- If in the opinion of the investigator continuation on study poses unreasonable risks to the patient. This might include patients who fail to return for adequate follow-up, hampering the ability to monitor toxicities

Any patient discontinuing study drug should be seen at 30 days post discontinuation for the evaluations outlined in the study schedule. The patient's tumor status should be assessed clinically and, if appropriate, disease progression should be confirmed by radiological assessment.

After discontinuation of the study medication at any point in the study, all ongoing AEs or SAEs must be followed until resolution unless, in the investigator's opinion the condition is unlikely to resolve due to the patients underlying disease, or the patient is lost to follow up. All new AEs and SAEs occurring during the 30 calendar days after the last dose of study medication must be recorded, reported if applicable and followed to resolution as above. Patients should be contacted at least 30 days after discontinuing study medication to collect and /or complete AE information. Any untoward event occurring subsequent to the 30-day follow-up AE reporting period that the investigator assesses as possibly related to the study medication should also be reported as an AE.

Any patient, who has not yet shown objective disease progression, should continue to be followed as per RECIST 1.1.

The study and/or individual Cohorts may be discontinued if it is found that it is not feasible to reach the planned outcomes.

13.1 Treatment Past Progression:

If a patient is found to have progression of disease by RECIST 1.1 criteria, but in the opinion of the treating clinician is felt to potentially still derive benefit, after discussion with study PI, the patient may consent to continue with protocol directed treatment. If the patient decides to continue receiving treatment, the patient will be asked to sign a separate consent form. The treating clinicans discussion of treatment past progression with the patient should be documented in the medical record.

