The objective response rate and progression free survival (PFS) will be analyzed separately for each disease type (basket/cohort 1,2,3 and4). PFS will be defined from the start of treatment to disease progression or death (whichever occurs first) or last follow-up. Kaplan Meier estimates will be used to estimate the median PFS and 2-year rate. Response will be determined by RECIST 1.1 criteria. Objective response is defined as complete or partial response by week 36 or best overall response. Duration of response will be reported for the subset of patients who experience an objective response. Clinical Benefit Rate (CBR) is defined as the percentage of patients who have achieved a complete response, partial response, or stable disease lasting ≥ 16 weeks.

Patients coming off study prior to first post-baseline assessment for reasons other than toxicity or progression may be replaced following discussion with study PI, if deemed appropriate. Patients who have measurable disease present at baseline, have received at least one cycle of therapy, and have had their disease re-evaluated will be considered evaluable for response Accrual in each cohort will continue until the required number of evaluable patients in each cohort are accrued. Responses will be confirmed by repeat imaging performed at least 4 weeks after confirmed response. Binomial proportions will be assumed when calculating the 2 sided 80% confidence interval around the objective response rate for each cohort separately.

To correlate the level of PR positivity (measured by immunohistochemsirty as a continuous variable), the level of phosphorylated PR (as a continuous variable) and the level of PR target gene expression (as a continuous variable) with response to therapy (defined as complete or partial response by week 36) with onapristone ER, a non-parametric test, such as the Wilcoxon test, will be used to test whether the PR levels (continuous variable) are different in the 2 groups of responders (complete or partial response) vs non responders. Each cohort/basket will be analyzed separately.

Sample Size:

Cohort 1 has enrolled 14 patients and stopped at Stage 1. Cohorts 2 (5 patinets enrolled) and 3 (1 patient enrolled) closed early due to poor accrual. Cohort 4 will enroll 14-23 patients. This study is expected to enroll between 34 and 43patients. Accrual of 1-2 patients per month is anticipated. The study is expected to complete accrual within 12-24 months.

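### PFS for event-free patients ends at last follow-up, a date not tied to a tumour assessment; the secondary 2-year PFS rate can be biased upward, by little if the planned progression follow-up works

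*Combined protocol and SAP*

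**What the plan says.** Section 14.0 (Biostatistics) defines the endpoint: "PFS will be defined from the start of treatment to disease progression or death (whichever occurs first) or last follow-up". Kaplan-Meier estimates of the median and the 2-year rate follow for each cohort. PFS is a secondary objective (Section 2.0).

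Other sections govern how progression is looked for:

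- **On treatment.** Section 9.1 schedules scans "every 8 weeks from Cycle 1 Day 1 while on treatment, and at end of study". Footnote 4 of the Section 10.0 schedule says: "Imaging should be performed every 8 weeks following Day 1 of treatment".
- **At exit.** The same footnote requires an end-of-treatment scan for patients leaving for reasons other than progression, if the last scan was more than 4 weeks earlier.
- **After treatment.** The Section 10.0 schedule has chart review for progression and survival status, each every 3 months, and no imaging mark. Footnote 12 reads: "Survival follow-up phone call will be conducted every 3 months from 30 day safety follow-up visit until the patient initiates a new treatment". For patients who stopped for toxicity or withdrew consent, "reviewing medical records for progression status will stop once the patient becomes POD".
- **Section 13.0.** "Any patient, who has not yet shown objective disease progression, should continue to be followed as per RECIST 1.1".

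**The concern.** Progression is established by imaging, but several contacts without imaging can fall after the last scan: the 30-day safety call, the survival calls, and a chart review that finds no new scan. If one of these sets the censoring date, the patient stays in the risk set as progression-free over a period in which nobody looked. Events missed in that period raise the Kaplan-Meier tail. The 2-year rate is exposed because it is read in the tail of cohorts of 14 to 23 patients, and a reader could not tell scan-confirmed from contact-only progression-free time.

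**Working it through.** **1. Whose date can drift from the last scan**

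- Patients who stop for progression already have an event.
- Patients still on treatment are scanned every 8 weeks and seen every 4 weeks after cycle 1, so the gap is at most about one scan interval. In a simulation where nobody stops without progression, the two censoring rules differed by 0.0 points.
- Patients who stop without progression can go on being contacted for months after the exit scan. The exposure is here.

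**2. Inputs**

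The plan states no expected median PFS, 2-year rate, dropout rate or capture rate, so it has no figure to reproduce. The inputs below are assumptions.

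- *p*, the share stopping without progression: 2.5% to 5.3%. The lower value is assumed. The upper is 1/19: in the first-line breast cancer study in Section 3.2, "one discontinued therapy after 4.5 months because of a marked elevation" in liver tests, while in stable disease. That is indirect evidence (immediate-release drug, other disease) and imprecise (exact 95% CI 0.1-26%).
- A lower value is arguable. Section 11.1 reports grade 3 events in 12 patients (16%), so about 12/0.16 = 75 patients, and two discontinuations for adverse events, both alongside progressive disease. Taking at most one as a stop without progression gives 1/75 = 1.3%.
- *c*, the share of these patients whose later progression is found at chart review or follow-up: 0 to 100%.

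**3. Simple ceiling**

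Suppose contact runs beyond 24 months. Each stopper with a missed progression is then counted as progression-free at 2 years. Apart from the short delay to the next chart review, the upward bias cannot exceed

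bias ≤ p × (1 − c), whatever the true median.

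| p | c = 90% | c = 50% | c = 0 |
|---|---|---|---|
| 1.3% | 0.13 | 0.65 | 1.3 |
| 2.5% | 0.25 | 1.25 | 2.5 |
| 5.3% | 0.53 | 2.65 | 5.3 |

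(percentage points)

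**4. Simulation against 8-weekly scans for everyone**

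Assumptions: exponential PFS with median 3, 6 or 12 months; p of 2.5% or 5.3%; exit scan if more than 28 days since the last; contact at 30 days, then 3-monthly for 6 to 24 months; 36-month cut-off; 200,000 patients per scenario. Bias of last-follow-up censoring in the 2-year rate, in points:

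| Off-treatment follow-up | Capture ≥ 90% | Capture ≥ 50% | No capture |
|---|---|---|---|
| Contact ends at new therapy (median 3-12 months) | −0.1 to +0.2 | −0.1 to +1.0 | 0.0 to +2.1 |
| No new therapy | −0.1 to +0.5 | −0.1 to +2.2 | +0.1 to +4.3 |

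If 8-weekly scans continue off treatment, the bias is within 0.03 of zero. A separate simulation with long contact gave about 0 at full capture, +0.1 to +0.5 at 90% and up to about +5 with none. These agree with the ceiling in step 3.

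**5. Scale**

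The binomial standard error of a 2-year rate is √(S(1 − S)/n).

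- Median 6 months: S = 0.5^(24/6) = 6.25%, SE 6.5 points (n = 14) or 5.0 (n = 23).
- Median 12 months: S = 0.5^(24/12) = 25%, SE 11.6 or 9.0 points.

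**6. Median**

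The Kaplan-Meier median did not move in any scenario of step 4.

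**7. The replacement rule, same inputs**

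Censoring at the last adequate assessment is within ±0.1 points when negative charted scans are counted. When only charted progressions are recorded it is biased downward, by up to about 0.7 points: the chart then adds late events but never extends event-free time.

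**The case against.** In a PFS definition, last follow-up is most naturally the last follow-up for progression. The exit scan, the chart review and Section 13.0 give that follow-up real content, so harm needs the literal reading and failed follow-up together. With at least 90% capture the error is far below the sampling error in step 5, and a carelessly applied replacement rule (up to −0.7) would be worse than the present one.

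Most of this stands, and it limits the size. It does not close the gap: the benign reading is not written down, footnote 12 creates contacts without imaging, and the choice of date would fall to the analyst. The point about the replacement rule is met by counting negative charted scans.

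A reader might also infer that Sections 9.1 and 13.0 contradict each other on imaging after treatment. They need not: Section 9.1 is the on-treatment plan and Section 13.0 covers patients who have stopped. What is missing is a cross-reference from the Section 10.0 schedule, which shows no off-treatment imaging.

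**Conclusion.** The point holds as a minor one. The stated rule lets unassessed time count as progression-free, and a standard rule does better. The bias in the 2-year rate is about 0 to 0.5 points if the planned follow-up works, and a few points (about 5 at most) if later progressions are largely missed, at 2.5-5.3% stopping and long contact. Those rates are assumptions. Cohorts 1 and 4 are affected; Cohorts 2 and 3, with 5 and 1 patients, give no useful 2-year rate in any case. The response endpoint and the Simon decisions do not use PFS. The median is essentially unaffected at these stopping rates.

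A reader might infer a serious inflation of PFS. Differences of up to about 16 points between the two rules do appear in simulation, but they need about 18-30% of patients leaving without progression, 24 months of contact and no progression found. The documents support none of these. Likewise, one missed patient could shift the rate by up to 1/14 = 7.1 or 1/23 = 4.3 points, but only if such a patient exists, is contacted for long enough and is never seen to progress.

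**What to change.** In Section 14.0, state that:

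- event-free patients are censored at the last adequate tumour assessment showing no progression, counting protocol scans and negative imaging documented at chart review;
- charted progressions and deaths remain events;
- last-follow-up censoring is reported as a sensitivity analysis.

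Cross-reference Sections 9.1 and 10.0 with Section 13.0 so that progression follow-up after treatment reads consistently. What that follow-up contains is for the sponsor to settle.

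Cost: a short addition to Section 14.0, and recording the dates of negative scans found at chart review. That recording is essential to avoid the downward bias in step 7. Fewer patients will be at risk in the tail, and some informative censoring may remain.

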9.2 Overview of Dose Adjustments for Onapristone ER Toxicity

Any dose modification of onapristone ER requires consultation with the study PI.

- If Grade 1 or 2 toxicities occur, give supportive care per institutional guidelines.
 No onapristone ER dose reduction should occur unless discussed with study PI.
- If ≥ Grade 3 toxicities occur that are considered potentially related to onapristone ER, including headache, nausea, vomiting, LFT elevation or diarrhea, hold

Memorial Sloan Kettering Cancer Center IRB Number: 19-061 A(9)

Approval date: 24-Apr-2023

onapristone ER until the toxicity resolves to ≤ Grade 1 (unless was Grade 2 at baseline, then when returns to baseline). If onapristone ER is held for LFT elevation, then LFT levels should be checked weekly until ≤ Grade 1 or baseline, and then onapristone ER resumed with dose reduction as per table below.

- If onapristone ER is held for ≤28 days it may be restarted at the same or a reduced dose at the discretion of the treating physician (except in the case of LFT elevation, which requires dose reduction).
- If onapristone ER is held for >28 days the drug should be permanently discontinued. Patients may continue on anastrozole as a single agent if onapristone ER is held Onapristone dose reductions will occur as per the table below:

Starting Dose	50 mg PO BID
Dose Reduction #1	30 mg PO BID
Dose Reduction #2	10 mg PO BID
Dose Reduction #3	Permanently Discontinue

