9.3 Dose Adjustment for Anastrozole Toxicity

No dose adjustments of anastrozole will occur.

- If Grade 1 or 2 toxicities occur, give supportive care per institutional guidelines.
- If ≥ Grade 3 toxicities occur that are considered potentially related to anastrozole (with the exception of osteoporosis or alopecia) hold anastrozole until the toxicity resolves to ≤ Grade 1 (unless was Grade 2 at baseline, then when returns to baseline).
- If anastrozole is held for ≤28 days, it may be restarted at the same dose at the discretion of the treating physician
- If anastrozole is held for >28 days, the drug should be permanently discontinued

Patients may continue on onapristone ER as a single agent if anastrozole is held

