12.1 Definitions

Evaluable for toxicity. All patients will be evaluable for toxicity from the time of their first treatment on study.

Evaluable for objective response. Only those patients who have measurable disease present at baseline, have received at least one cycle of therapy, and have had their

disease re-evaluated will be considered evaluable for response. These patients will have their response classified according to the definitions stated below. (Note: Patients who exhibit objective disease progression prior to the end of cycle 1 will also be considered evaluable.)

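### Early toxicity stops: the replacement rule implies they stay in the Cohort 4 count, but the evaluability and accrual rules drop and replace them, biasing the response rate slightly upward

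*Combined protocol and SAP*

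**What the plan says.** Section 14.0 deals with early leavers in one sentence: "Patients coming off study prior to first post-baseline assessment for reasons other than toxicity or progression may be replaced following discussion with study PI". Toxicity and progression are carved out, so by implication a patient who leaves for either reason is not replaced. The sentence names no denominator.

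Two sentences later the same section says: "Accrual in each cohort will continue until the required number of evaluable patients in each cohort are accrued". Section 12.1 defines evaluability for response: "Only those patients who have measurable disease present at baseline, have received at least one cycle of therapy, and have had their" disease assessed again. Its one exception is: "Patients who exhibit objective disease progression prior to the end of cycle 1 will also be considered evaluable". Section 14.0 repeats the definition without that exception. Neither place provides for toxicity, death or clinical decline.

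For Cohort 4, section 14.0 sets at least 1/14 responses to expand and at least 3/23 to succeed. The rates are 3% versus 20%, with type I error 5% and type II error 15%. A two-sided 80% confidence interval is planned for the response rate, and planned enrolment is 14 to 23.

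Four other provisions decide who ends up without a scan:
- Imaging is due "every 8 weeks from Cycle 1 Day 1 while on treatment" (9.1).
- An end-of-treatment scan is done for patients leaving for reasons other than progression, "only if it has been greater than 4 weeks since the last tumor assessment" (10.0, note 4).
- Each drug may be held for up to 28 days and restarted. In Cohort 4, "Patients may continue on anastrozole as a single agent if onapristone ER is held" (9.2) and "Patients may continue on onapristone ER as a single agent if anastrozole is held" (9.3).
- Patients without objective progression stay in RECIST follow-up after stopping drug (13.0).

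**The concern.** Take a Cohort 4 patient who stops both drugs for toxicity during cycle 1. The replacement sentence implies that she keeps her place. The evaluability definition excludes her because she has not completed a cycle, and the accrual rule then enrols someone else, which is replacement in effect. Nothing in the document reconciles the two. A later toxicity stop, a death or a clinical decline with no post-baseline scan is also not evaluable.

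These patients are almost certainly non-responders, so leaving them out can only raise the observed rate and its interval relative to an all-treated rate. Stage I is sensitive because it turns on a single response. Suppose one of the first 14 treated stops for toxicity in cycle 1 and the only responder is the 15th treated. Counting the early stop gives 0/14 and the cohort stops. The evaluable rule gives 1/14 and the cohort expands. Both readings can be defended from the current text, in an open-label trial.

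**Working it through.** **1. Reproduce the design.** The inputs are the Cohort 4 figures in 14.0. The probability of success at response rate p is

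f(p) = Σ (x = 1 to 14) P(X₁ = x) · P(X₂ ≥ max(0, 3 − x)), with X₁ ~ Bin(14, p) and X₂ ~ Bin(9, p).

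- p = 0.03: 0.2827 × 0.0282 + 0.0568 × 0.2398 + 0.0077 = 0.0293.
- p = 0.20: 0.1539 × 0.5638 + 0.2501 × 0.8658 + 0.5520 = 0.8553.

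These meet the stated 5% and 85%. A full search returns the same minimax design.

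**2. Exclusion rate q.** This is the share of treated patients left out as non-evaluable, all taken as non-responders. The documents give no such rate for the combination. Section 3.1 reports two discontinuations due to adverse events at any time among 31 + 52 = 83 patients: 2/83 = 2.4%. One was for unrelated events, the other for disease progression/liver test abnormalities. It is a rough proxy; 5% and 10% are assumptions.

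**3. Operating characteristics, one rate basis at a time.** The documents do not say which population 3% and 20% refer to.

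(a) Both are all-treated rates. Counting early stops keeps 2.9% and 85.5%. The evaluable-only rule gives f(p/(1 − q)). For example, at q = 0.05, 0.03/0.95 = 0.0316 and f = 0.0333.

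(b) Both are evaluable-patient rates. The evaluable-only rule keeps 2.9% and 85.5%. Counting early stops gives f(p(1 − q)).

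| q | (a) evaluable-only: type I error | (a) power | (b) early stops counted: type I error | (b) power |
|---|---|---|---|---|
| 2.4% | 3.1% | 86.7% | 2.75% | 84.3% |
| 5% | 3.3% | 88.0% | 2.6% | 82.8% |
| 10% | 3.8% | 90.3% | 2.2% | 79.7% |

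Under (a), type I error reaches 5% at q = 0.192.

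**4. Chance that the two rules give different stage I decisions.** With pₑ the rate among evaluable patients (p or p/(1 − q)), this is [q + (1 − q)(1 − pₑ)]¹⁴ − (1 − pₑ)¹⁴.

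| q | rate 3% | rate 20% |
|---|---|---|
| 2.4% | 0.7% | 0.4% |
| 5% | 1.4–1.5% | 0.7–0.8% |
| 10% | 2.9–3.1% | 1.4–1.8% |

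**5. Effect on the estimate.** With one exclusion at the success boundary, 3/23 = 13.0% (exact 80% interval 4.9–26.8%) becomes 3/24 = 12.5% (4.7–25.8%).

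**6. Enrolment figures.** The total of 34 to 43 is 14 + 5 + 1 + 14 to 14 + 5 + 1 + 23. It leaves no room for patients beyond the Simon numbers, although the accrual rule would require them whenever someone is not evaluable.

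**The case against.** The strongest reply is that the conflict rests on inference. The replacement sentence is permissive and never says outright that toxicity stops are not replaced, and no sentence names the denominator for the response rate or its interval. One could read the early-leaver sentence as the specific rule and the accrual sentence as the general one, which would keep toxicity stops in the count. Enrolment equal to the Simon numbers, and Cohort 1 reported as 14 enrolled with stable disease in 9 of 14, fit that reading.

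The affected group is also narrow. Holds, continuation on one drug and dose reductions before a toxicity discontinuation (13.0) make a complete stop in cycle 1 uncommon. A stop after cycle 1 can become evaluable through an end-of-treatment or follow-up scan, and 12.4.3 asks for efforts to document objective progression after treatment ends. The 2.4% is not an early-toxicity rate, and no stated error rate is breached at the rates examined.

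Much of this stands, and it is why the effect is judged small. It does not remove the conflict. Section 12.1 words evaluability exclusively and rescues only objective progression, which blocks the specific-over-general reading. The enrolment range conflicts with the accrual sentence and so does not settle the matter. The Cohort 1 figures are uninformative if every patient there was evaluable. The remedy does go somewhat beyond toxicity, but death and clinical decline without a scan fall into the same gap.

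**Conclusion.** The concern holds and is minor. The replacement sentence and the evaluability and accrual rules treat an early toxicity stop differently, and following the latter biases the Cohort 4 response rate upward relative to an all-treated rate. The direction follows from the excluded patients being non-responders.

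The size is likely small. On an all-treated basis, type I error moves from 2.9% to 3.1–3.8% for exclusion of 2.4–10%, below the stated 5%. On an evaluable-patient basis there is no inflation. The two rules would disagree at stage I in about 0.7% to 3.1% of trials at a 3% rate.

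This rests on three assumptions: that non-replacement is what the carve-out means, that the evaluable count is the denominator for the rate and interval, and that the exclusion rates, which the documents do not supply, are in this range.

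**What to change.** State in 14.0 and 12.1 that, for the 14 and 23 in the Simon rule and for the 80% confidence interval, treated patients who leave before the first post-baseline assessment because of toxicity, progression (objective or clinical) or death count as non-responders and are not replaced. Reword the accrual sentence to match. Report the response-evaluable set as a sensitivity analysis.

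This is a text change to the counting rule only. The reported response rate will be slightly lower. If 20% is an all-treated rate, no power is lost. If it is an evaluable-patient rate, power is 84.3% at 2.4% such dropouts and 82.8% at 5%, instead of 85.5% (stated 85%).
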